Data Analyses: Baseline demographics and descriptive variables (e.g., age, gender, pain duration) will be summarized for each of the two treatment conditions. Descriptive summaries for continuous variables will be presented in terms of means and standard deviations while discrete variables will be summarized in terms of relative frequencies and percentages. For aim one, latent growth curve modeling will be performed. This approach is most effective for analyzing change over time, as well as capturing individual differences across all three time-points (baseline CPX assessment, midpoint self-report session, post exercise training CPX assessment). This approach does not assume a linear trajectory and is thus ideal for the current proposal. According to Needham, Espel, Adler and Kiefe⁷⁷ with this approach, the latent growth curve analysis will use repeated measures of each construct in order to estimate the underlying growth trajectory by computing the intercept and the slope, also known as the latent factors. The intercept can also be considered the starting point or baseline and the slope is the rate of change across time.

Aim 1 : Hypothesis one will be evaluated by conditional LGMs. The Intercept of the LGM will be centered on the self report data from the baseline CPX assessment (i.e., first Slope loading will be fixed to 0.0). The intermittent time point (midpoint self-report session) will be freely estimated and the final time point (i.e the self-report data from the 13 week MAX-EX test session) will have a corresponding Slope factor loading fixed to 1.0. Accordingly, the mean and variance of the Slope factor will convey the fixed (average) and random effects (individual differences) of change for the time interval of interest. The two study groups will be dummy coded (using chronic pain/PTSD as the reference condition in the initial models) and included as predictors in the LGM to account for individual differences in symptom reduction (i.e. pain intensity, pain tolerance and threshold, depression and PTSD symptoms) due to treatment assignment. The Intercept will be regressed onto the treatment covariates to examine any pre-exercise training differences among treatment conditions. Moreover, individual differences in pre-treatment functioning will be held constant by regressing the Slope onto the Intercept. Hypotheses 1 will be supported in part by the statistical significance of the study group (dummy code) > Slope paths. In fact, these paths reflect study group x Time interaction effects. The nature of these interaction effects in the LGMs will be characterized using the procedures described by Curran, Bauer, and Willoughby.⁷⁸ All outcome measures will be analyzed in this fashion.

Aims 2 & 3: At both exercise assessment time-points, change scores will be computed ALLO+PA and these will be correlated with pain tolerance and pain threshold scores using Pearson or Spearman correlations, as appropriate. For exploratory purposes, ALLO+PA will be used as predictor variables in a regression equation to predict pain outcome (tolerance, threshold and intensity).

Exploratory Aim: Pearson or Spearman correlations, as appropriate, will be computed to assess interrelationships among ALLO+PA exercise motivation, self-efficacy, pain sensitivity, severity and disability, PTSD severity, and depression. Based on the findings of these correlations, biological (ALLO +PA) and/or psychological markers (e.g., self-determination or self-efficacy for exercise) will be entered as predictors in separate multiple regression equations to predict pain sensitivity, pain-related disability, PTSD and depression.

Limitations: The proposed study has several limitations that may be addressed in future research. First, this study does not consider other types of chronic pain conditions (i.e. neuropathic and fibromyalgia). Second, potential effects of additional forms of exercise (i.e. weight training) are not taken into account in a rigorously quantitative way, though we will consider this variable more qualitatively in data analyses. Third, the impact of phase of the menstrual cycle cannot be studied given the time and financial resources available; instead we have elected to study all menstruating women during the follicular phase and

perimenopausal/menopausal women who are within our target age range. During this phase, estrogen and progesterone levels are low and stable and approximate levels seen in men. In addition, previous studies suggest that pain sensitivity is greatest for women during this phase and published data from [name] laboratory has shown cerebrospinal fluid allopregnanolone levels in women with PTSD to be substantially lower than in healthy controls during this phase. Finally, the duration and intensity of the exercise component needed to induce changes in the neurobiological parameters of interest is a factor that will have to be considered in greater detail in future studies based in part on pilot data to be collected in the current study.

(c) Human Studies Section

(1). Risk to Subjects:

(a) Human Subjects Involvement and Characteristics: Participants in the proposed research project will be participants who are currently receiving care at VABHS. Due to the lower rates of women in the VA system, women participants will also be recruited from the community since it is often difficult to recruit the required number of women Veterans, among the four study groups, in order to conduct gender comparisons. In addition, while we plan to recruit the majority of our male participants from the VA, when there is also a similar difficulty in recruiting the required number of men Veterans, we will also recruit from the community. The eligibility criteria is as follows: Participants will be 30 participants receiving care in the VABHS or recruited from the community. Inclusion criteria for the proposed study will permit the recruitment of men and women, at least 18 years of age, who are from all ethnic and racial backgrounds, and able to speak and understand English. The patient population at the VABHS is 65% Caucasian, 15% African American, 10% Latino, and 10% Asian. We anticipate that a substantial percentage of the sample will be members of minority groups who are widely served by the VABHS.

Inclusion Criteria: Only participants in whom a physical examination, medical history, EKG, and baseline laboratory studies including urine toxicology screens indicate that maximum load exercise testing will be safe will be included in this study. Participants must be free of medications and other substances (e.g., illicit drugs and alcohol) with effects that could hinder data interpretation for 2-6 weeks depending on the medication and frequency of use (which must be cleared by the PI's primary mentor). If on pain medications with short half-lives, must be off of them for 5 half-lives before testing, generally about 24 hours. Any participant with an ICD9 chronic pain diagnosis, with a musculoskeletal etiology, as confirmed by [name], will be allowed for inclusion in the study. Also, any participant with a confirmed psychiatric diagnosis of PTSD (PTSD/chronic pain group), or have trauma exposure without a diagnosis of PTSD, other psychiatric conditions, or chronic pain will also be included in the study. Individuals with PTSD must meet for current chronic PTSD (≥ 3 months) as assessed by the CAPS 1-Month Diagnostic Version.

Exclusion criteria: Participants will be excluded from participation in the study if they have a life threatening or acute physical illness (e.g., cancer), current schizophreniform illnesses or bipolar disorder, or active suicidal or homicidal ideation requiring clinical intervention. Women participants who are pregnant or are intending to become pregnant within the next six months, will be excluded from participation. Individuals with current or past alcohol and/or substance dependence (less than three months from date of screening assessment) will be excluded. Individuals seeking pain treatment such as surgical interventions or who have a neuropathic

originto their pain or fibromyalgia will also be excluded. Participants with chronic pain concerns that cannot tolerate exercising in a reclining bike and those who have had a clinical history of coronary artery disease or positive stress test, uncontrolled cardiac arrhythmia, moderate-to-severe aortic stenosis, severe arterial hypertension (systolic >200 mmHg, diastolic>110 mm Hg) and more than first degree atrioventricular block also will be excluded from participation.

(b) Sources of Materials: A significant source of the data from participants will come from the data that they supply as part of their involvement in this trial (e.g. outcome measures completed by participants). Additional information will come from review of the participant's medical record. The National Center for PTSD-Behavioral Sciences Division maintains an electronic database of potential research participants. The database contains relevant screening information from participants and non-patient research participants seen in the PTSD Clinic (e.g., medication status, age, years of education, etc.). Participant entry into the database is done on a voluntary basis and written consent for future contact has already been established. The system currently contains data on over 350 potential research participants. As indicated in the research plan, we also plan on collecting plasma samples in order to measure ALLO+PA and other steroids of interest pre and post exercise and cold pressor test sessions. We will only use such samples for purposes of conducting the present research and no existing samples will be used. We will only use these biological samples from non-Veterans when we recruit non-Veterans from the community because it is difficult to recruit the required number of men and or women among the four study groups and meet the current eligibility and inclusion criteria.

(c) Potential Risks: The potential physical, psychological or other risk to participants who participate in the proposed research study characterized as minimal. Since participants will be completing questionnaires and receiving an exercise test, there is a slight possibility that some participants may experience psychological discomfort in reflecting on his or her own medical and psychological health conditions. The PI, as a trained clinical psychologist, will be able to provide thorough assessment in the event of a participant's adverse reaction to the questioning and/or intervention. Appropriate intervention and/or referral for more intensive treatment can be provided, if needed. There are additional physical risks associated with the exercise and cold pressor test session which are outlined in the "**Protection Against Risk**" section below as well as our plan to minimize such risks. No other known physical, social or legal risk associated with participation in the proposed research project is identified.

(2). Adequacy of Protection From Risks:

(a) Recruitment and Informed Consent: Issues related to recruitment and obtaining informed consent is relevant to the proposed study. Informed consent will be obtained by the PI or trained research technician at the pre-treatment assessment session. A witness, who is a VA staff member but no identified on the study protocol, will be available to witness the consent. It will be obtained from all study participants prior to participation, according to the institutional guidelines established by the Institutional Review Board (IRB) at the VABHS. Following the completion of the informed consent form, the consent form will be given to the research technician for photocopying for the participant copy as well as scanned into the participant's VA medical record. All participants who

decline the study or do not meet study criteria will be given feedback on the evaluation results and offered an alternative treatment (e.g., PTSD treatment and/or pain management offered through the VABHS or if non-Veteran, a referral to an outside provider).

The information contained within the consents form will include:

- Invitation to participate because the patient meets the criteria for pain and/or PTSD or are trauma exposed but do not meet criteria for pain and/or PTSD.
- Estimated time to complete the screening eligibility session (4 hours) as well as the exercise and cold pressor test session (~4.5 hours)
- Participation is voluntary
- Description of each study procedure (i.e. psychiatric screen, physical exam, lab work, EKG, exercise maximum load test, cold pressor pain threshold test, etc).
- Statement of the freedom to withdraw at anytime without adverse effects on their healthcare at VABHS.
- Description of potential discomforts, risks and inconveniences as well as our plan to minimize such risks.
- No personal benefit will come from participation in the research.
- Participation in research is not necessary to receive care through the pain or PTSD centers at VABHS.
- Amount of compensation provided for participation in each study session.
- Contact information for the PI (copy of consent will be provided to subject)

(b) Protection Against Risk: The primary risk associated with the proposed research plan includes psychological distress resulting from increased focus on ones' medical and psychological health problems within the context of individual interviews about such problems. To address the risk associated with psychological distress that may occur, the PI is a trained clinical psychologist who will be in a good position to provide further evaluation of the patient's distress. This evaluation may include contact with a patient's current healthcare providers, including mental health professionals, if needed. The PI will also be in a good position to make recommendations for further evaluation and/or treatment, and to ensure that such consults are placed on the patient's behalf. In addition, all participants will be provided with the PI's contact information, and encouraged to establish contact as needed. In the event of suicidal or homicidal ideation, a credentialed psychiatrist or a psychologist will evaluate any patient who reports suicidal or parasuicidal or homicidal ideation or behavior at any point during the study and refer the participant for further evaluation and treatment if indicated, against the participants will if necessary. Lastly, in the case of homicidal ideation with explicit intent to harm a named individual, the PI will report the intent to the local police as legally required to protect the named individual. The PI will contact

the participant's mental health provider (if they have one). The participant will be reminded to contact their VA providers, the suicide prevention coordinator, or the Veteran's Suicide hotline if he or she feels at risk in the future.

**Due to the nature of the exercise and cold pressor test session, there are additional risks that we have identified as well as devised a plan to minimize such risks:(1) Blood Drawing and IV Placement: Blood drawing and placement of an IV may be associated with bruising, pain, infection, or rarely, fainting. Sterile equipment and technique by used by qualified personnel while the subject is seated or lying will minimize this risk. The amount of blood sampled during this study over 4 months will be about 240 cc (or about 16 tablespoons which is equal to approximately 1/2 of a standard blood donation).

(2) Breathing mouthpiece: The breathing mouthpiece worn during exercise testing may be uncomfortable. In addition, saliva will tend to accumulate in the subject's mouth when the mouthpiece is in place. This may lead to drooling and will be uncomfortable until subjects have figured out how to swallow with the mouthpiece in place.

(3) Cold Pressor Test: While the experience of pain is an expected part of this procedure, participants will be informed during the consent process that there will be a time limit imposed (without full disclosure of the actual time limit—7 minutes) and are therefore not at risk of freezing or other related injuries to their hand.

(4) Exercise Testing:

- a). Men may need to have parts of their chest hair shaved in order to attach electrodes; this hair grows back over the next few weeks.
- b). Exercise assessments (clinical treadmill and cardiopulmonary exercise testing) all require people to apply themselves with great effort. Although encouragement and careful medical supervision will help to make these tests as agreeable as possible, some people might still find it unpleasant.
- c). Maximal exercise testing is generally associated with a 1 in 10,000 chance of a bad reaction (heart attack or dying). In unselected populations, which include persons referred for exercise testing because of cardiac symptoms, the risk of myocardial infarction or death from exercise testing is approximately 1 in 2500. Specifically, the risk of death has been estimated at <0.01%. In an asymptomatic patient population, selected to have no history, signs, or symptoms of coronary artery disease (as in this study), the risk of harm would be expected to be even lower. However, all those enrolled will have a physical exam immediately before to best insure they are stable and they will have a cardiologist or nurse supervising the performance of the stress test to be sure they are maximally safe and well cared for if any problems develop in accordance with routine VA patient care protocols.

- d). The exercise physiologist and Cardiologist/Nurse Practitioner completing the test will be ACLS certified (Advanced Cardiac Life Support). Performance of the testing in the VABHS, Jamaica Plain Clinical Studies Unit (CSU) will allow immediate access to a code cart and defibrillator. Tests will only be completed when the VABHS Code team is also immediately available.
- e). Other problems that might also develop from a stress test include heart rhythm abnormalities and skin reactions to the electrode leads. The cardiologist or nurse will administer care for any problem that may arise and coordinate with the subjects' doctors (as long as release of information is provided if the subject is a non-VA patient).
- f). It should be pointed out that clinical cardiac stress tests and the experimental maximum load exercise testing described in this protocol are similarly stressful to the myocardium. In addition, the criteria for stopping the maximum load exercise testing are the same as those for the clinical cardiac stress testing. Both tests take participants to maximum "volitional" exercise load unless EKG changes, BP changes, or other symptoms suggest that the participant should end exercise testing prematurely.

(5). Exercising at home:

We anticipate that the same risks during the exercise tests apply to the exercise prescriptions performed at home. However, in both the informed consent and through verbal discussion with each participant, we will encourage them to call 911 or go to the nearest emergency room for evaluation if they experience any chest pain or unusual shortness of breath or weakness while exercising at home. With respect to the chronic pain participants, we will encourage them to call the PI immediately if they experience any unusual, intense increase in their pain intensity levels during or after exercising, in order to be evaluated by [name] so that he can provide a recommendation for modification of their exercise prescription as needed. Finally, we will also encourage all participants to call us if they experience any physical injury while exercising at home so they too can receive further evaluation by [name] and modification of their exercise prescription and/or a referral for follow-up care by their primary care doctor (both inside and outside VABHS).

(6) Increase in Anxiety or PTSD Symptoms in Response to Exercise: Some PTSD patients participating in other exercise tests published by other investigators have been reported to have experienced an increase in intrusive thoughts or other reexperiencing symptoms or anxiety in response to exercise. Some patients with PTSD report that this can occur during or in response to everyday attempts to exercise as well. Subjects will be told that they can stop exercising if this occurs. In addition, the PI and primary mentor, [name], the psychiatrist present at the exercise testing, will talk with the subject to determine whether any additional treatment should be offered to help with such symptoms. The subject will be instructed to call the Biostudies Unit during the day or the VA operator to get the Biostudies psychiatrist on call after hours if an increase in PTSD or anxiety symptoms persists or occurs after the subject has left the VA. Finally,

while participants are exercising at home, they will be encouraged to call the PI if they experience any increase in their psychological symptoms during or after exercising. The PI will then be able to determine if further intervention is needed.

(7) Harm to the Fetus (Women Only): Cardiac exercise tests or the experimental maximum load exercise testing could cause harm to a developing fetus. Thus an effective method of birth control must be used during enrollment in the study. In addition, urine pregnancy tests will be performed at screening and on the day of exercise testing.

Confidentiality: The confidentiality of the information that is gathered from participants (audiotaped interviews, questionnaires) will be protected through secure storage of such media in a locked cabinet in the PI's office. Additionally, this information will be de-identified for the purposes of analysis and dissemination of findings.

**The probability of ALL of the above stated risks is expected to be low, and the steps detailed, should they be needed, are expected to be effective in minimizing and or reducing such risks.

(3). Potential Benefit of the Proposed Research to the Subject and Others:

The proposed study is consistent with VHA National Pain Management Strategy and overall mission of the National Center of PTSD, which assures that all persons cared for in the VA healthcare system can reliably count on prompt and appropriate treatment of pain and psychological distress. The proposed study seeks to evaluate the efficacy of a potential treatment that may reduce suffering from comorbid pain and PTSD and improve quality of life, overall health and well-being for our Veterans. The proposed study will address the specific objectives of the National Pain Management Strategy and mission of the National Center of PTSD and will directly address the care of participants with PTSD and chronic pain, both high priority problems within the VA.

In addition participants who participate will provide valuable information about the understudied role of exercise in the potential treatment of chronic pain and PTSD. This information will help to inform the further development and refinement of an individualized exercise treatment as well as a motivationally based exercise behavior change intervention to promote long-term exercise adherence, for individuals suffering from chronic pain and PTSD. Thus, there is considerable potential benefit for the proposed research to indirectly help research participants and others who also suffer from chronic pain and PTSD.

(4). Importance of Knowledge to be Gained: Given the high prevalence of both pain and PTSD among Veterans, particularly the high co-prevalence of these two conditions, the current research is important in that it marks a first step toward a more psychologically and neurobiologically based look at the role exercise may play in the treatment for these conditions. More specifically, the proposed research will potentially identify exercise as one mechanism that may serve to moderate or mediate the shared factors that maintain the co-prevalence of these conditions. The delineation of the role of exercise will help to inform new

treatment approaches for comorbid pain and PTSD. One such example is the potential for the development of an exercise behavior change protocol, rooted in the most evidenced-based motivational theories to date, that can either be integrated into the existing cognitive-behavioral interventions or used as an adjunctive treatment by counselors specialized in health behavior change, thereby improving the efficacy of these interventions for this population.

(5) Resources

(a) Research Space:

(1) The proposed research will be conducted in VA space at VABHS.

(b) Other Research Resources:

The National Center for PTSD, Behavioral Science Division (BSD) at Boston, Massachusetts, under the direction of [name] PhD, the academic advisor of the proposed study, as well as the Women's Health Science Division (WHSD), under the direction of [name], a consultant of the proposed study, is at the forefront of efforts to develop effective assessment devices and treatment for PTSD. Current investigations address both psychological and psychophysiological procedures. In addition, the Division staff is engaged in research on basic mechanisms of PTSD as related to cognitive information processing, family and social support factors, and gender issues. Studies of behavioral treatment process and outcome comprise a third major focus of the Division research. Training activities of the Division emphasize both research and clinical skills. [name] has also been provided with office space to use at the VABHS, WHSD throughout the duration of this study.

The VA Boston Healthcare System (VABHS) Center for Pain Management, directed by mentor [name], of the proposed study, is a clinical, research, and training center that has the full and continuing support of referring physicians throughout VISN 1. The Center functions as one program among a broad array of psychology programs within Medical Psychology available to practitioners and participants. Over the past several years, the Medical Psychology Section has established an effective collaborative interface with the primary care clinical settings and providers. [name] will have access to all primary care facilities at the VABHS and has the support of the Service Line Manager of primary care to recruit participants for her research.

The Clinical Studies Unit (CSU), directed by mentor, [name], M.D. is located on the 11th floor, C wing, of the VABHS building. HEAL exercise testing lab is 150 square feet and it is adjacent to the Clinical Studies Unit which provides four 150 square foot rooms that can be signed out for exams, assessment and interviews. Also located on the wing is a 1600 square foot cardiac and pulmonary rehabilitation and research exercise suite. Additionally located directly above this facility are research staff offices. [name] will coordinate scheduled exercise testing sessions with the exercise physiologist and the lab will be accessible for the duration of the scheduled exercise test sessions (8am-12:30pm) and supervised exercise sessions, as well as weekly check-in sessions during the

“progressive training program. During this time, [name] will have access to the adjacent CSU exam room for her staff to be able to prep the study participant prior to the actual exercise test procedure (i.e. IV set-up and electrode placement) as well as supervised exercise sessions. In fact the cold pressor test sessions will be conducted in this so as to control for room temperature and noise. By collaborating with mentors involved in the CSU lab, this will provide opportunities to establish longer-term collaborations as additional grant mechanisms are awarded and will contribute to the overall infrastructure and running of the CSU lab services.

References:

1. [name], J. D., [name], T. M., Kerns, R. D. (2003). An examination of the relationship between chronic pain and post-traumatic stress disorder. *Journal of Rehabilitation Research & Development*, 40(5), 397-405. doi:10.1682/JRRD.2003.09.0397
2. Scioli, E. R., [name], J. D., [name], T. M. (2010). Psychological problems associated with OEF/OIF deployment. *American Journal of Lifestyle Medicine*, 4(4), 349-359. doi:10.1177/1559827610362962
3. Shipherd, J. C., Keyes, M., Jovanovic, T., Ready, D. J., Baltzell, D., Worley, V.,...Duncan, E. (2007). Veterans seeking treatment for posttraumatic stress disorder: what about comorbid chronic pain?. *Journal of Rehabilitation Research & Development*, 44(2), 153-166. doi:10.1682/JRRD.2006.06.0065
4. Beckham, J. C., Crawford, A. L., Feldman, M. E., Kirby, A. C., Hertzberg, M. A., Davidson, J. R. T.,...Moore S. D. (1997). Chronic post-traumatic stress disorder and chronic pain in Vietnam combat Veterans. *Journal of Psychosomatic Research*, 43(4), 379-389. doi:10.1016/S0022-3999(97)00129-3

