Cold Pressor Test (CPT): Measures of pain sensitivity will be obtained using the CPT, a procedure that has been used widely in laboratory studies to measure pain perception and tolerance,⁷⁰ as well as self-report measures of pain severity and disability and exercise motivation (Appendix 1). The cold pressor protocol will follow guidelines from a previously published study investigating similar variables.⁷⁰ Chronic pain mentor [name], who has experience administering the cold pressor test, will provide supervision. Participants will be instructed to hold their right hand in temperature-controlled ice water, inside a cold pressor apparatus, up to their wrist and to keep the hand still. They will be instructed to say when they first experience pain and will be told to withdraw their hand when the pain becomes intolerable. Therefore two measures of pain sensitivity will be derived: "pain threshold" and "pain tolerance". Pain threshold is defined as the number of seconds between hand immersion in the ice water and the first report of "pain." Pain tolerance is defined as the number of seconds between hand immersion and hand withdrawal from the water. A maximum seven-minute time limit for immersion, unknown to the patient, will be imposed. The CPT will be obtained: A) in relation to the acute maximum load exercise assessment (pre- and post-CPX), and B) in relation to progressive exercise training (before, at mid-point, and after completion).

A) Participants will perform baseline pain ratings and the CPT in the late morning **one to five days before** each CPX, two and a half hours after IV placement and the breakfast of power bars provided. Blood will be sampled from the IV for ALLO+PA measurement just prior to the pain ratings and CPT. Participants will have fasted since midnight, as per procedures for the CPX. The post-CPX pain ratings and CPT will be performed on the day of the CPX, immediately after the 30' post-CPX blood drawing for ALLO+PA. Obtaining the baseline and post-CPX pain assessments at the same time of day on two separate days will control for potential effects of diurnal variation on pain sensitivity, as well as ALLO+PA levels.

B) The procedures in A will be completed before and after completion of the chronic exercise training program.

C) In addition, the baseline pain ratings and CPT procedures in A will be performed at the mid-point of the progressive exercise training program.

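### Taken literally, the Aim 1 growth model's time-points mix post-exercise and resting cold pressor values, and the plan does not say which cold pressor reading enters the model

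*Combined protocol and SAP*

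**What the plan says.** The Data Analyses section gives the Aim 1 waves as "capturing individual differences across all three time-points (baseline CPX assessment, midpoint self-report session, post exercise training CPX assessment". The Aim 1 paragraph then sets the loadings:

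- Baseline: "The Intercept of the LGM will be centered on the self report data from the baseline CPX assessment", with the first slope loading set to zero.
- Midpoint: "The intermittent time point (midpoint self-report session) will be freely estimated".
- Endpoint: the self-report data from the week-13 maximal test session "will have a corresponding Slope factor loading fixed to 1.0".

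The modelled outcomes are "symptom reduction (i.e. pain intensity, pain tolerance and threshold, depression and PTSD symptoms", and the paragraph closes by applying the same treatment to every outcome measure. It makes no exception for the cold pressor test.

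The Cold Pressor Test (CPT) section sets out when the test is done. Under item A a resting test takes place in a separate session one to five days before each CPX. For the second test, "The post-CPX pain ratings and CPT will be performed on the day of the CPX", directly after the blood draw at 30 minutes post-exercise. Under item C, "the baseline pain ratings and CPT procedures in A will be performed at the mid-point of the progressive exercise training program". The Chronic Pain Measures list agrees: pre-exercise tests belong to the cold pressor sessions, and post-exercise tests to the exercise sessions.

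**The concern.** Aim 1 asks whether symptoms change over 12 weeks of training. Aim 3 asks how a single bout of maximal exercise alters pain sensitivity. A cold pressor time recorded after a maximal test carries both effects; one recorded at rest carries only the first. If waves 1 and 3 come from the CPX day and wave 2 from the midpoint session, the three values do not measure the same thing.

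The protocol itself expects the acute effect. Hypothesis 3a presupposes that acute exercise lowers pain sensitivity and raises tolerance. Hypothesis 3b sets the endpoint pain response against the pre-training one. The Summary at the end of the Background proposes that patients at first lack the pain-relieving benefit of exercise and gain it through training. If that is right, a rise in the acute response could be reported as a training gain in pain tolerance although resting sensitivity had not moved.

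**Working it through.** **Step 1. Which cold pressor reading falls at each stated wave**

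| Aim 1 wave | Slope loading | Cold pressor test at that visit | State |
|---|---|---|---|
| Baseline CPX | 0 | after CPX, following the 30-minute draw | post-exercise |
| Midpoint session | free (λ) | resting procedure repeated | resting |
| Endpoint CPX | 1.0 | after CPX, following the 30-minute draw | post-exercise |

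The resting tests that pair with waves 1 and 3 exist, but at a different session.

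**Step 2. Algebra**

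Let R1, R2, R3 be the mean resting values at baseline, midpoint and endpoint. Let A1 and A3 be the mean acute post-exercise shifts at the two CPX visits. The expected wave means are R1 + A1, R2 and R3 + A3. The model writes them as I, I + λS and I + S. Equating the two:

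- Intercept: I = R1 + A1
- Slope: S = (R3 − R1) + (A3 − A1)
- Midpoint loading: λ = (R2 − R1 − A1) / S

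This matches means only. Constraints on residual variances, or group predictors, would also let the covariances pull on λ.

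**Step 3. Illustration**

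The plan states no figure to reproduce here, and no cold pressor effect for training or for acute exercise. All values below are assumptions. Take R1 = 0, R2 = 0.5, R3 = 1, so that the unit is the resting gain over training.

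| A1 | A3 | Intercept | Slope | λ |
|---|---|---|---|---|
| 0 | 0 (resting at all waves) | 0 | 1.00 | 0.50 |
| 0.25 | 0.25 | 0.25 | 1.00 | (0.5 − 0.25)/1 = 0.25 |
| 0.5 | 0.5 | 0.5 | 1.00 | 0.00 |
| 1 | 1 | 1 | 1.00 | −0.50 |
| 0 | 0.5 | 0 | 1.50 | 0.5/1.5 = 0.33 |
| 0.25 | 0.5 | 0.25 | 1.25 | 0.25/1.25 = 0.20 |
| 0.5 | 0.25 | 0.5 | 0.75 | 0.00 |

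When A1 = A3 the slope is untouched; the intercept and λ are not. When the acute effect changes, the slope is wrong by exactly A3 − A1, in either direction. The row with A1 = 0 is closest to the Background's account of patients who at first get no acute benefit. With no resting change at all (R1 = R2 = R3) and A1 = 0.25, A3 = 0.5, the slope is 0.5 − 0.25 = 0.25, all of it acute response.

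**Step 4. Group paths**

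The difference in slope between groups is the difference in R3 − R1 plus the difference in A3 − A1. The second term vanishes if the acute response changes equally in both groups.

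**Step 5. Intercept as covariate**

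The plan regresses slope on intercept to hold pre-treatment functioning constant. Here the intercept contains A1 and the slope contains −A1. Their covariance therefore includes Cov(A1, A3) − Var(A1), taken across individuals, which has nothing to do with resting pain sensitivity.

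**The case against.** The strongest reply is that the plan never says the post-exercise reading is used. The Aim 1 paragraph ties waves 1 and 3 to self-report data, and the CPT section treats the cold pressor test as distinct from self-report measures. The same section gives the test two purposes: before and after the CPX for acute exercise, and before, midway through and after training for the training effect. Only the resting reading is collected at all three of those stages, so it is the natural candidate for Aim 1, and the CPX label may be loose shorthand for the paired sessions. Table 2, the assessment timeline, was not in the text available here, which calls for some caution.

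Much of this stands. A reader might infer that the plan instructs use of post-exercise values; the documents do not support that. A reader might also infer that acute effects always inflate the training slope. They do not: a stable effect cancels. Nor can Hypothesis 2a be cited for a changing pain response, since it concerns ALLO+PA levels, and Hypothesis 3b is framed as a correlation and not as a mean change.

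What does not stand is that the text settles the matter. Cold pressor times are listed in the model, every outcome is put through the same time-points, and nothing assigns the resting series to Aim 1. The self-report label does not exclude the test either, because the midpoint self-report session includes one. At best, two eligible readings surround each CPX and the choice is left open.

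**Conclusion.** The concern holds as a specification defect. The stated time-points, taken at their word, give post-exercise, resting and post-exercise values for tolerance and threshold. On that reading the intercept is shifted by A1, the midpoint loading is distorted even when the acute effect is constant, and the mean slope is biased by A3 − A1. The protocol's own hypotheses give reason to expect that A3 − A1 is not zero. Leaving aside the contaminated intercept adjustment, the group-to-slope paths are biased only if that change differs by group.

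The size of the bias cannot be taken from the documents, and the figures above show only its form. Tolerance and threshold are the only outcomes clearly affected. Depression and PTSD questionnaires are completed before exercise on the CPX day, and the numerical pain rating asks about the past week. Data collection is adequate; only the analysis text needs repair.

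**What to change.** State in the Aim 1 paragraph that, for pain tolerance and threshold, all three waves come from the resting cold pressor sessions: the one before the baseline CPX, the midpoint, and the one before the endpoint CPX. State under Aims 2 and 3 that the post-CPX readings are used only for Aim 3, as post-CPX minus resting change at each time-point. In the same edit, say which of the several same-day numerical and McGill ratings enters Aim 1.

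The cost is a few sentences, ideally settled before outcome data are examined. No visit, test or participant burden is added, because all of these tests are already scheduled.
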